**4.2.2. Other Secondary Objectives**

Other Secondary These are prespecified objectives that will not be adjusted for multiplicity	
Objectives	Endpoints
To test the hypothesis that baricitinib 4-mg + TCS, baricitinib 2-mg + TCS, or baricitinib 1-mg + TCS is superior to placebo + TCS in the treatment of moderate-to-severe AD	
 
Proportion of patients achieving IGA of 0 or 1 with a <math>\geq 2</math>-point improvement at Week 4 and Week 52
 
Proportion of patients achieving EASI75 at Week 4 and Week 52
 

To compare the efficacy of baricitinib 4-mg + TCS, baricitinib 2-mg + TCS, or baricitinib 1-mg + TCS to placebo + TCS in AD during the double-blind placebo-controlled treatment period as measured by improvement in signs and symptoms of AD	
 
Proportion of patients achieving EASI50 at 16 weeks
 
Proportion of patients achieving IGA of 0 at 16 weeks
 
Mean change from baseline in SCORAD at 16 weeks
 
Proportion of patients achieving SCORAD90 at 16 weeks
 
Mean change from baseline in BSA affected at 16 weeks
 
Proportion of patients developing skin infections requiring antibiotic treatment by Week 16
 
Mean number of days without use of background TCS over 16 weeks
 
Mean gram quantity of background TCS used over 16 weeks (tube weights)
 

To compare the efficacy of baricitinib 4-mg + TCS, baricitinib 2-mg + TCS, or baricitinib 1-mg + TCS to placebo + TCS in AD during the double-blind placebo-controlled treatment period as assessed by patient-reported outcome measures	
 
Percent change from baseline in Itch NRS at Week 52, Week 24, Week 16, Week 4, and Week 1
 
Proportion of patients achieving a 4-point improvement in Itch NRS at 24 weeks
 
Mean change from baseline in the total score of the POEM at 16 weeks
 
Mean change from baseline in the PGI-S-AD scores at 16 weeks
 
Mean change from baseline in HADS total scores at 16 weeks
 
Mean change from baseline in the DLQI total scores at 16 weeks
 
Mean change from baseline in the WPAI-AD total scores at 16 weeks
 
Mean change from baseline in the EQ-5D-5L total scores at 16 weeks
 

Substudy: Randomized Downtitration These are prespecified objectives that will be not be adjusted for multiplicity	

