- Proportion of patients achieving a  $\geq 4$ -point improvement in POEM total score for those with a baseline total score  $\geq 4$

HADS (including Week 52):

- Proportion of patients achieving a HADS Anxiety Score  $< 8$  for those with a baseline HADS Anxiety Score  $\geq 8$
- Proportion of patients achieving a HADS Depression Score  $< 8$  for those with a baseline HADS Depression Score  $\geq 8$
- Proportion of patients achieving improvement in HADS Anxiety Score or HADS Depression Score  $< 8$  for those with a baseline HADS Anxiety Score  $\geq 8$  or a baseline HADS Depression Score  $\geq 8$
- Change from baseline in HADS total score

BSA at Week 52:

- Mean change from baseline in BSA affected

Itch NRS at Week 52:

- Proportion of patients achieving a 4-point improvement in Itch NRS

Skin infections at Week 52:

- Proportion of patients developing skin infections requiring antibiotic treatment

Mean number of days without use of background TCS over 52 weeks

Mean gram quantity of background TCS used over 52 weeks (tube weights)

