### **6.2.3. Derived Data**

- Age (year), derived using first dose date as the reference start date and July 1 of birth year and truncated to a whole-year (integer) age. Patients whose derived age is less than 18 will have the required minimum age of 18 at informed consent; however, reporting for age, age groups, and laboratory ranges, will be based on the derived age.
- Age group (<65 years,  $\geq$ 65 years)
- Age group (<65 years,  $\geq$ 65 years to <75 years,  $\geq$ 75 years to <85 years,  $\geq$ 85 years)
- Body mass index (BMI) ( $\text{kg}/\text{m}^2$ ) = weight ( $\text{kg}$ )/((height ( $\text{cm}$ )/100) $^2$ )
- BMI category (<25  $\text{kg}/\text{m}^2$ ,  $\geq$ 25  $\text{kg}/\text{m}^2$  to <30  $\text{kg}/\text{m}^2$ ,  $\geq$ 30  $\text{kg}/\text{m}^2$ )
- The duration of AD from diagnosis (years) = [(date of informed consent – date of AD diagnosis )+1]/ 365.25.
  - If year of onset is missing, duration of AD will be set as missing. Otherwise, unknown month will be taken as January, and unknown day will be taken as 01. The duration of AD will be rounded to 1 decimal place.
- Duration of AD (years) category (0 to <2 years, 2 years to < 5 years, 5 years to <10 years, 10 years to <20 years,  $\geq$ 20 years)
- Diagnosis age (years), derived using diagnosis date as the reference start date and July 1 of birth year and truncated to a whole-integer age
- Diagnosis age group (<18,  $\geq$ 18 to <50,  $\geq$ 50 years old)
- Change from baseline = postbaseline measurement at Visit x – baseline measurement
  - If a baseline value is missing, it will not be imputed and the change from baseline will not be calculated.
- Percent change from baseline at Visit x:  
((postbaseline measurement at Visit x - baseline measurement)/baseline measurement)\*100.
  - If a baseline value is missing, it will not be imputed and percent change from baseline will not be calculated.
- Weight ( $\text{kg}$ ) = weight ( $\text{lb}$ ) \* 0.454.

- Weight category (<60 kg,  $\geq$ 60 kg to <100 kg,  $\geq$ 100 kg)
- Height (cm) = height (in) \* 2.54.
- Cyclosporine inadequate efficacy (yes, no)
  - Set **yes** if the reason for discontinuation is inadequate response.
- Cyclosporine intolerance (yes, no)
  - Set **yes** if the reason for discontinuation is intolerance to medication or contraindication (physician indicated cyclosporine was used and a contraindication was noted).
- Cyclosporine contraindication [ineligible] (yes, no)

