Patient Global Impression of Severity-Atopic Dermatitis (PGI-S-AD)	The (PGI-S-AD is a single-item question asking the patient how they would rate their overall AD symptoms over the past 24 hours. The 5 categories of responses range from “no symptoms” to “severe.” Refer to Section 6.2.2 for details on how to calculate the weekly score which will be used in the continuous analysis.	
 
PGI-S-AD score
 
Change from baseline in PGI-S-AD
 
	
Single item. Range 1 to 5. Refer to Section 6.2.2 on how to derive the visit score.
 
Change from baseline: observed PGI-S-AD score – baseline PGI-S-AD score
	
Refer to Section 6.2.2 on how to derive the visit score.
 
Missing if baseline or observed value is missing.

Hospital Anxiety Depression Scale (HADS)	The HADS is a 14-item self-assessment scale that determines the levels of anxiety and depression that a patient is experiencing over the past week. The HADS utilizes a 4-point Likert scale (eg, 0 to 3) for each question and is intended for ages 12 to 65 years (Zigmond and Snaith 1983; White et al. 1999). Scores for each domain (anxiety and depression) can range from 0	
 
HADS score for anxiety and depression domains
 
Change from baseline in HADS domain
 
Change from baseline in HADS total
 
	
Anxiety domain score is sum of the seven anxiety questions, range 0 to 21; Depression domain score is sum of the seven depression questions, range 0 to 21.
 
Change from baseline: observed HADS domain score – baseline HADS domain score
 
Change from baseline: observed HADS domain score – baseline HADS total score
	
N/A – partial assessments cannot be saved.
 
Missing if baseline or observed value is missing.
 
Missing if baseline or observed value is missing.

Measure	Description	Variable	Derivation / Comment	Imputation Approach if with Missing Components

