Work Productivity and Activity Impairment: Atopic Dermatitis (WPAI-AD)	The WPAI-AD records impairment due to AD during the past 7 days. The WPAI-AD consists of 6 items grouped into 4 domains: absenteeism (work time missed), presenteeism (impairment at work/reduced on-the-job effectiveness), work productivity loss (overall work impairment/absenteeism plus presenteeism), and activity impairment. Scores are calculated as impairment percentages (Reilly et al. 1993), with higher scores indicating greater impairment and less productivity.	
 
Employment status
 
Change in employment status
 
Percentage of absenteeism
 
Change from baseline in absenteeism
 
Percentage of presenteeism
 
Change from baseline in presenteeism
 
Overall work impairment
 
Change from baseline in work impairment
 
Percentage of impairment in activities
 
	
Q1
 
Employed at baseline and remained employed: Q1 = 1 at post-baseline visit and at baseline visit. Not employed at baseline and remain unemployed: Q1 = 0 at post-baseline visit and at baseline visit.
 
Percent work time missed due to problem: <math>(Q2/(Q2 + Q4)) * 100</math>
 
Change from baseline: observed absenteeism – baseline absenteeism
 
Percent impairment (reduced productivity while at work) while working due to problem: <math>(Q5/10) * 100</math>
 
Change from baseline: observed presenteeism – baseline absenteeism
 
Percent overall work impairment (combines absenteeism and presenteeism) due to problem: <math>(Q2/(Q2+Q4)) + [(1 - Q2/(Q2+Q4)) * (Q5/10)] * 100</math>
 
Change from baseline: observed work impairment – baseline work impairment
 
Percent activity impairment (performed outside of work) due to problem: <math>(Q6/10) * 100</math>
	
Single item, missing if missing.
 
Missing if baseline or observed value is missing.
 
If Q2 or Q4 is missing, then missing.
 
Missing if baseline or observed value is missing.
 
If Q5 is missing, then missing.
 
Missing if baseline or observed value is missing.
 
If Q2, Q4, or Q5 is missing, then missing.
 
Missing if baseline or observed value is missing.
 
If Q6 is missing, then missing.

Measure	Description	Variable	Derivation / Comment	Imputation Approach if with Missing Components

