	• 1.5-point improvement on Item 2 of ADSS	Logistic regression using NRI (primary censoring rule)	ITT	Bari 4-mg or Bari 2-mg or Bari 1-mg vs PBO; Week 16	Exploratory Analysis
Patient-Oriented Eczema Measure (POEM) [continuous]	• POEM score change from baseline	MMRM (censoring rule #1 at Week 16 and #2 at Week 52)	ITT	Bari 4-mg or Bari 2-mg or Bari 1-mg vs PBO; Week 16, 52	Secondary analysis for Week 16
		ANCOVA; mLOCF (censoring rule #1 at Week 16 and #2 at Week 52)	ITT	Bari 4-mg or Bari 2-mg or Bari 1-mg vs PBO; Week 16, 52	Sensitivity analysis

Measure	Variable	Analysis Method (Section 6.2.2.2)	Population (Section 6.2.1)	Comparison a /Time Point	Analysis Type
Patient-Oriented Eczema Measure (POEM) [categorical]	
 
Proportion of Patients achieving an MCID of POEM improvement <math>\geq 3.4</math>
 
Proportion of Patients achieving an MCID of POEM improvement <math>\geq 4</math>
 
	Logistic regression using NRI (censoring rule #1)	ITT	Bari 4-mg or Bari 2-mg or Bari 1-mg vs PBO; Week 16	Exploratory analysis
Patient Global Impression of Severity–Atopic Dermatitis (PGI-S-AD)	
 
PGI-S-AD score change from baseline
 
	MMRM (censoring rule #1 at Week 16 and #2 at Week 52)	ITT	Bari 4-mg or Bari 2-mg or Bari 1-mg vs PBO; Week 16, 52	Secondary analysis for Week 16
		ANCOVA; mLOCF (censoring rule #1 at Week 16 and #2 at Week 52)	ITT	Bari 4-mg or Bari 2-mg or Bari 1-mg vs PBO; Week 16, 52	Sensitivity analysis
Hospital Anxiety Depression Scale (HADS)	
 
HADS change from baseline in domain scores:           
 
- anxiety
 
- depression
 
 
 
	MMRM (censoring rule #1 at Week 16 and #2 at Week 52)	ITT	Bari 4-mg or Bari 2-mg or Bari 1-mg vs PBO; Week 16, 52	Secondary analysis for Week 16
		ANCOVA; mLOCF (censoring rule #1 at Week 16 and #2 at Week 52)	ITT	Bari 4-mg or Bari 2-mg or Bari 1-mg vs PBO; Week 16, 52	Sensitivity analysis

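### Three derivations in SAP Table JAIN.6.10 are wrong as printed: overall work impairment, change in presenteeism and change in HADS total

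*SAP*

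**What the plan says.** Table JAIN.6.10 in SAP Section 6.11 sets out how each health-outcome variable is calculated. Three of its lines are in question.

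- **Overall work impairment (WPAI-AD).** After an opening parenthesis, the formula reads "Q2/(Q2+Q4)) + [(1 - Q2/(Q2+Q4)) * (Q5/10)] * 100". The row calls the result a percentage that combines absenteeism and presenteeism. The measure's description, like Protocol Section 9.1.3.9, says the scores are percentages on which higher is worse. The separate absenteeism and presenteeism rows are each multiplied by 100.
- **Change in presenteeism.** It is given as "Change from baseline: observed presenteeism – baseline absenteeism".
- **Change in HADS total.** It is given as "observed HADS domain score – baseline HADS total score". The table defines the anxiety and depression domain scores, each 0 to 21, but no total.

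The SAP's general rule in Section 6.2.3 is "Change from baseline = postbaseline measurement at Visit x – baseline measurement".

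Section 4.2.2 lists "Mean change from baseline in the WPAI-AD total scores at 16 weeks" and "Mean change from baseline in HADS total scores at 16 weeks" as other secondary endpoints, without multiplicity adjustment. Section 4.3 lists "Change from baseline in HADS total score" again as exploratory, including Week 52. Table JAIN.6.11 gives presenteeism and overall work impairment a secondary MMRM at Week 16, as observed values and as changes. For HADS its change analyses cover only "HADS change from baseline in domain scores".

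**The concern.** A change score should compare a variable with its own baseline. Two of the lines do not, although the neighbouring rows for absenteeism, work impairment, activity impairment and the HADS domains do. The work impairment formula mixes scales: absenteeism enters as a fraction from 0 to 1, and presenteeism enters as a percentage.

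The consequences differ if the lines are followed literally:

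- The work impairment error is directional. It counts against whichever arm has less absence from work.
- The presenteeism error shifts every within-arm change and is likely to add noise. It should not bias the comparison of randomised arms in expectation, because baseline absenteeism is balanced by randomisation. The analysis of observed presenteeism is unaffected.
- The HADS error leaves one domain's treatment effect out of the total.

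**Working it through.** The plan states no figure to reproduce here, so the check evaluates the printed lines against the SAP's own definitions. Patient and arm values below are illustrative assumptions.

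**Overall work impairment.** Let A = Q2/(Q2+Q4) and P = Q5/10.

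- Printed: A + 100(1 − A)P
- On a percentage scale: 100[A + (1 − A)P]
- Correct minus printed: 100A − A = 99A, whatever Q5 is
- Slope of the printed score in A: 1 − 100P. This is negative for any Q5 of 1 or more. At Q5 = 0 the score rises only from 0 to 1.

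| Q5 | Absenteeism | Printed | Correct |
|---|---|---|---|
| 0 | 0 / 25 / 50 / 75% | 0 / 0.25 / 0.5 / 0.75 | 0 / 25 / 50 / 75 |
| 1 | 0 / 25 / 50 / 75% | 10 / 7.75 / 5.5 / 3.25 | 10 / 32.5 / 55 / 77.5 |
| 5 | 0 / 25 / 50 / 75% | 50 / 37.75 / 25.5 / 13.25 | 50 / 62.5 / 75 / 87.5 |

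One patient, Q5 fixed at 5, going from 50% absence to none: the printed change is 50 − 25.5 = +24.5 (worse), and the correct change is 50 − 75 = −25 (better).

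Two arms, treating each arm as a patient at its mean, with absenteeism of 15% on placebo and 5% on active:

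- Equal presenteeism of 40%. Printed: placebo 0.15 + 100 × 0.85 × 0.4 = 34.15; active 0.05 + 100 × 0.95 × 0.4 = 38.05; difference +3.9. Correct: 49 and 43; difference −6.0.
- Equal presenteeism of 20% or 60%. Printed differences are +1.9 and +5.9; correct differences are −8 and −4.
- Presenteeism of 40% on placebo and 30% on active. Printed: 0.05 + 100 × 0.95 × 0.3 = 28.55, and 28.55 − 34.15 = −5.6. Correct: 33.5 − 49 = −15.5.

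Every case is wrong by 99 × 0.10 = 9.9 points. Absenteeism differences of 5 and 20 points give errors of 4.95 and 19.8.

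**Change in presenteeism.** Presenteeism unchanged at 50 with baseline absenteeism 10 gives 50 − 10 = +40 instead of 0. An improvement from 60 to 30 with the same baseline absenteeism gives 30 − 10 = +20 instead of −30.

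**Change in HADS total.** Take the total as anxiety plus depression, range 0 to 42. The printed line equals the correct change minus the observed score of the domain left out.

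- Unchanged at 10 + 10: 10 − 20 = −10 instead of 0.
- Worsening from 6 + 5 to 12 + 9: 12 − 11 = +1 using anxiety, or 9 − 11 = −2 using depression, instead of 21 − 11 = +10.
- A true advantage of 2 points in each domain over the comparator shows as 2 instead of 4.

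**The case against.** The case against concedes the wording and disputes its weight.

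- **The arm-level sign reversal rests on equal presenteeism.** This is right. In the example above, the printed active score drops below placebo once active presenteeism is under (34.15 − 0.05)/95 = 35.9%, so a gain of about 4.1 points removes the reversal. The 9.9-point error against the arm with less absence remains.
- **A lost outer bracket pair could explain the first formula.** This cannot be fully excluded, although the printed brackets balance. The other two are wrong words, which text extraction would not plausibly produce.
- **The HADS line feeds no tabulated change analysis and does not say which domain to use.** Both points are fair, and other specifications may exist that we cannot see. But HADS total change is a declared endpoint, and this line is its only specific derivation in the SAP. The mismatch between a total endpoint and domain-only change rows is itself a gap.
- **SAP Version 5 governs the final lock, and Table JAIN.6.12 has no WPAI-AD or HADS rows.** This is also fair. The main practical value therefore lies in checking programs used for earlier locks.
- **Items 2 and 3 are evident slips.** The intent can indeed be inferred from adjacent rows and Section 6.2.3. The SAP is still the text that programs are validated against.

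**Conclusion.** The concern holds. All three lines give wrong results if followed as printed. The work impairment shortfall of 99A is exact and needs no assumption about the data. Whether it would reverse the direction of an arm comparison depends on how presenteeism differs between arms. The HADS figures assume that the total is the sum of the two domains.

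The effect is confined to WPAI-AD and HADS total, which are not multiplicity-controlled. The HADS domain changes are derived correctly, and the primary and key secondary endpoints are unaffected. The documents do not show whether the programs followed the printed text, so no claim is made that any reported result is wrong. Correction is warranted because these are analysis rules for declared endpoints, and the first error is directional.

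**What to change.** Amend Table JAIN.6.10:

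- Overall work impairment = 100 × {Q2/(Q2+Q4) + [1 − Q2/(Q2+Q4)] × Q5/10}, after confirming the brackets in the source SAP.
- Change in presenteeism = observed presenteeism − baseline presenteeism.
- Define HADS total as anxiety plus depression, and change in HADS total = observed total − baseline total.

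In the same edit, add a HADS total change row to Table JAIN.6.11 so that the listed endpoint has an analysis. Then check the derivation programs used at the interim locks against the corrected text.

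The cost is three text corrections, one definition, one table row and a program check. If the programs followed the printed lines, the Week 16 WPAI-AD tables and any HADS total tables at Week 16 or 52 need a rerun.

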9.1.3.9. Work Productivity and Activity Impairment Questionnaire–Atopic Dermatitis

The Work Productivity and Activity Impairment Questionnaire–Atopic Dermatitis (WPAI-AD) records impairment due to AD during the past 7 days. The WPAI-AD consists of 6 items grouped into 4 domains: absenteeism (work time missed), presenteeism (impairment at work/reduced on-the-job effectiveness), work productivity loss (overall work impairment/absenteeism plus presenteeism), and activity impairment. Scores are calculated as impairment percentages (Reilly et al. 1993), with higher scores indicating greater impairment and less productivity.

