	
 
Observed and Change from baseline in:
 
	MMRM (censoring rule #1)	ITT	Bari 4-mg or Bari 2-mg or Bari 1-mg vs PBO; Week 16	Secondary analysis

Measure	Variable	Analysis Method (Section 6.2.2.2)	Population (Section 6.2.1)	Comparison a /Time Point	Analysis Type
	
 
- absenteeism
 
- presenteeism
 
- overall work impairment
 
- activity impairment
 
	ANCOVA; mLOCF (censoring rule #1)	ITT	Bari 4-mg or Bari 2-mg or Bari 1-mg vs PBO; Week16	Sensitivity analysis
European Quality of Life-5 Dimensions-5 Levels (EQ-5D-5L)	
 
• Observed values in 
 
- EQ-5D mobility
 
- EQ-5D self-care
 
- EQ-5D usual activities
 
- EQ-5D pain/ discomfort
 
- EQ-5D anxiety/ depression
 
 
 
	Logistic Regression using NRI (censoring rule #1)	ITT	Bari 4-mg or Bari 2-mg or Bari 1-mg vs PBO; Week 16	Exploratory Analysis
	
 
• Observed and Change from baseline in 
 
- EQ-5D VAS
 
- EQ-5D-5L UK Population-based index score
 
- EQ-5D-5L US Population-based index score
 
 
 
	
 
MMRM (censoring rule #1)
 
ANCOVA; mLOCF (censoring rule #1)
 
	
 
ITT
 
ITT
 
	
 
Bari 4-mg or Bari 2-mg or Bari 1-mg vs PBO; Week16
 
Bari 4-mg or Bari 2-mg or Bari 1-mg vs PBO; Week 16
 
	
 
Secondary analysis
 
Sensitivity analysis
 

Medical Outcomes Study 36-Item Short Form Health Survey Version 2 Acute (SF-36)	
 
• Observed and Change from baseline in summary scores: 
 
- MCS (mental component score)
 
- PCS (physical component score)
 
 
 
	MMRM & ANCOVA; mLOCF (censoring rule #1)	ITT	Bari 4-mg or Bari 2-mg or Bari 1-mg vs PBO; Week 16	Exploratory analysis

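### Overall work impairment is set to missing when Q5 is blank, even for a patient who missed all work hours, for whom the SAP's formula gives the maximum score whatever Q5 is

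*SAP*

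**What the plan says.** SAP Section 6.11, Table JAIN.6.10, derives the WPAI-AD domains from numbered items.

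- Absenteeism is described as "Percent work time missed due to problem" and computed as Q2/(Q2 + Q4) on a percentage scale. Its missing-data rule is "If Q2 or Q4 is missing, then missing", so Q5 plays no part.
- Presenteeism is Q5/10 as a percentage, described as "Percent impairment (reduced productivity while at work) while working due to problem".
- Overall work impairment combines the two, printed (after an opening bracket) as "Q2/(Q2+Q4)) + [(1 - Q2/(Q2+Q4)) * (Q5/10)] * 100". Its missing-data rule is "If Q2, Q4, or Q5 is missing, then missing".

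Table JAIN.6.11 lists "overall work impairment" as a secondary analysis at Week 16: MMRM under the primary censoring rule, with ANCOVA on mLOCF data as a sensitivity analysis. SAP Section 4.2.2 places WPAI-AD among the other secondary objectives, outside multiplicity control.

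**The concern.** The missing-data rule asks for Q5 in a case where the formula does not use it. A patient who worked no hours has no at-work productivity to rate, so a blank Q5 is plausible for that patient. The rule would then discard a score that Q2 and Q4 already fix at its worst value.

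The planned methods would not restore it:

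- The MMRM (SAP Section 6.3.2) assumes data are missing at random, whereas here the gap would follow from the current, worst value.
- mLOCF (Section 6.3.3) would put an earlier post-baseline score in its place.
- If the gap falls at baseline, Section 6.2.3 gives the patient no change score at any visit.

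**Working it through.** **Inputs.** The formula and both missing-data rules come from Table JAIN.6.10. Because absenteeism is Q2/(Q2 + Q4), Q2 is work time missed because of AD and Q4 is work time done. The documents give no rate of full-week absence and no WPAI-AD means, so all rates and means in step 4 are assumptions. The SAP states no figure to reproduce here.

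**1. Formula on the intended percentage scale.** Let a = Q2/(Q2 + Q4). Then score = 100 × [a + (1 − a) × Q5/10].

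**2. Some hours worked.** Q2 = 20, Q4 = 20 gives a = 0.5. The score is 50, 75 and 100 for Q5 = 0, 5 and 10. Q5 matters, and requiring it is right.

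**3. No hours worked.** Q2 = 40, Q4 = 0 gives a = 1 and 1 − a = 0. The score is 100, 100 and 100 for Q5 = 0, 5 and 10. Q2 = 8, Q4 = 0 gives the same. Taken literally, the printed brackets apply the factor 100 only to the second term, so the printed result is 1.0 for each Q5. That is a separate slip, and Q5 has no influence in either reading. The rule nevertheless returns missing if Q5 is blank, while absenteeism for the same patient and visit is 100%.

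If Q2 = Q4 = 0, a is 0/0 and undefined. The SAP does not address this case.

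**4. Possible size, on assumed values.** Let s be the share of an arm's scorable patients with Q4 = 0 and Q2 > 0, all with Q5 blank, and m the mean of the others. Dropping the 100% scores lowers the arm's observed visit mean by s × (100 − m):

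| s | m = 20 | m = 30 | m = 40 |
|---|---|---|---|
| 1% | 0.8 | 0.7 | 0.6 |
| 2% | 1.6 | 1.4 | 1.2 |
| 5% | 4.0 | 3.5 | 3.0 |
| 10% | 8.0 | 7.0 | 6.0 |

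For the treatment difference, assume the other patients average 40 on placebo and 25 on baricitinib. The observed difference is then 15 in every case.

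- 5% placebo, 1% baricitinib fully absent: placebo 0.05 × 100 + 0.95 × 40 = 43.00; baricitinib 0.01 × 100 + 0.99 × 25 = 25.75. The difference with these patients scored is 17.25, so dropping them understates it by 2.25.
- 2% in both arms: placebo 0.02 × 100 + 0.98 × 40 = 41.2; baricitinib 0.02 × 100 + 0.98 × 25 = 26.5. The difference is 14.7, so dropping them overstates it by 0.3.

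These are raw visit means. The endpoint is change from baseline, so absences at baseline would also enter, and the MMRM would recover whatever other visits predict.

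**The case against.** The strongest objection is that nothing in the documents shows the rule is ever triggered. The WPAI-AD items are not reproduced, no skip is described, and the wording of Q5 is a scoring description. The existence of item-level missing rules does not settle it. For EQ-5D the same table gives such rules for the single dimensions, yet says for the index that incomplete questionnaires cannot be stored on the tablet. The rule also has an ordinary use, for patients who are not employed. This stands: a blank Q5 at zero hours is an inference, and the finding is conditional on it. It does not make the rule right for that case.

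Three stronger readings are tempting, and the documents do not support them.

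- **That the worst patients leave the endpoint.** A post-baseline gap loses one visit's value of one WPAI-AD domain. Absenteeism is analysed separately at Week 16 and keeps the patient at 100%. The questionnaire is scheduled at Weeks 0, 1, 2, 4, 8, 12 and 16, so the patient can still contribute to the MMRM through other visits. Only a baseline gap removes every change score.
- **That the bias runs in a known direction.** Step 4 shows that the treatment difference can be understated or overstated, depending on the split between arms.
- **That the employment display cannot show a change, or that a patient who lost a job looks the same as one with no questionnaire.** The table does define only the unchanged groups, for example "Not employed at baseline and remain unemployed: Q1 = 0 at post-baseline visit and at baseline visit". But the change variable is missing only when one of the two employment answers is missing. A patient who lost a job has both and is not missing. Observed employment status is also displayed, per Table JAIN.6.11. What remains is two transition categories without labels.

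**Conclusion.** The concern holds as a minor defect in a derivation. For Q2 > 0 and Q4 = 0 the SAP's missing-data rule conflicts with its own formula: it can discard a score that recorded answers fully determine. That part rests on algebra alone.

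Whether it affects results depends on Q5 being left blank when no hours were worked, which the documents do not state, and on how many patients were fully absent, which is unknown. The 0.6 to 8.0 point range for an arm's mean is illustrative only. The consequence is confined to an other-secondary, unadjusted Week 16 analysis; the primary and key secondary conclusions do not depend on it.

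**What to change.** Replace the missing-data rule for overall work impairment in Table JAIN.6.10 with three cases:

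- If Q4 = 0 and Q2 > 0, the score is 100% regardless of Q5.
- If Q2 + Q4 = 0, absenteeism and overall work impairment are both missing.
- Otherwise, the score is missing if Q2, Q4 or Q5 is missing.

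Report the number of visits affected, by arm. If Q5 is never blank at zero hours, the first case changes nothing, and the count will show that.

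The rule uses only items already collected and does not depend on treatment. The cost is one derivation line and a rerun of the Week 16 output. SAP Section 6.16 says the 24-week interim analysis has been done, so the rerun should be documented as a later correction and shown beside the planned result.

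As a minor clarification only, label the two employment transitions: employed at baseline and not employed afterwards, and the reverse.
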